4.1.2 The CXCL12/CXCR4 Axis in Acute Myeloid Leukemia

Normal CD34⁺CD38⁻ HSCs migrate to and are anchored in the bone marrow by chemotactic signals produced by cells in the marrow stroma (8,9,10,11). Foremost of these signals is the CXC chemokine CXCL12 (stem cell derived factor-1), which ligates chemokine receptor 4 (CXCR4) on the HSC surface. This signaling activates directional Rho/Rac-mediated migration toward and attachment in the bone marrow environment through enrichment of pseudopodia with adhesion receptors such as very late antigen-4 and others. CXCL12/CXCR4 signaling also activates phosphatidylinositol-3-kinase and its downstream effector protein kinase B, providing enhanced survival (10). In the marrow, HSCs shuttle between an endosteal osteoblastic niche inducing quiescence and a sinusoidal endothelial vascular niche promoting proliferation and differentiation (8). Recent evidence suggests that quiescence in the endosteal niche is maintained by close association with megakaryocytes (12,13). Megakaryocytes negatively regulate HSC proliferation through secretion of platelet factor-4 (PF4), which also enhances integrin-mediated endothelial adhesion during bone marrow homing (14).

There is substantial evidence that LSCs employ the same CXCL12-, CXCR4-, adhesion molecule-dependent mechanisms as normal HSCs to home toward a marrow niche and maintain themselves in a quiescent, protected state (8,14,15,16,17,18,19,20,21,22,23). CXCR4 is an unfavorable prognostic marker in AML (24,25,26,27,28), and its high expression on CD34⁺ AML is associated with the poor survival in patients with Fms-like tyrosine kinase-3 /internal tandem duplication mutations. Conversely, disrupting CXCR4 signaling inhibits transmigration, survival and chemotherapy resistance *in vitro* (29,30,31,32) and tumor growth in AML xenografts (32,33,34,35). Clinical experience with the CXCR4 inhibitor Plerixafor in AML is just beginning (36,37). Short term daily subcutaneous administration of Plerixafor for up to 7 days for stem cell mobilization is well tolerated (38). However, cardiac toxicity arose when it was administered as a daily intravenous (IV) infusion or subcutaneous injection for 11-14 days (39). This questions

the safety of long term continuous blockade of CXCR4, a receptor also important in repair of injured tissues.

An alternative approach to blocking CXCR4 signaling is direct interference with its ligand CXCL12. Heparin, a glycosaminoglycan used as an anticoagulant, avidly binds to a cluster of cationic amino acids on the CXCL12 surface that overlaps with the CXCR4 binding region (40,41). Heparin inhibition of CXCL12 is diminished by removal of 6-O, but not 2-O sulfates (42), but is apparent only at concentrations of 20 U or approximately 3 µg/mL (42,43), which exceed therapeutic heparin plasma levels for anticoagulation by 10-fold (44). Low anticoagulant 2-O, 3-O desulfated heparin (ODSH, also known as CX-01, Figure 6—2) is a porcine intestinal heparin derivative that retains many heparin anti-inflammatory properties. Additionally, CX-01 binds PF4 with affinity similar to heparin, but the CX-01/PF4 complex does not bind antibodies that produce platelet activation and mediate heparin-induced thrombocytopenia (HIT). Furthermore, megakaryopoiesis is negatively regulated by PF4 and anti-PF4 blocking antibodies diminish chemotherapy-induced thrombocytopenia (CIT) in mice. CX-01 binds to and reverses biologic activities of PF4 and mitigates CIT in transgenic mice that overexpress PF4.

Based on these considerations, we conducted a pilot study combining CX-01 with standard chemotherapy for the treatment of AML. Results, as described below, suggest that CX-01 increases the complete remission (CR) rate and enhances count recovery. In addition, we show that CX-01 potently inhibits CXCL12 ligation of CXCR4 *in vitro* at concentrations that do not produce anticoagulation.

4.1.3 Clinical Strategies to Block CXCR4

A number of strategies have been tested to block CXCR4, among these are AMD3100 (Genzyme), BKT140 (Biokine Therapeutics), MSX-122 (Med Koo Biosciences), unfractionated heparin (UFH) and LMWH (various).

AMD3100 (known as Plerixafor and Mozobil), has gained Food and Drug Administration approval for the mobilization of stem cells. AMD3100, when used with another small molecule CXCR4 inhibitor, BKT140, acts synergistically with chemotherapy in human non-small cell lung cancer under experimental conditions (45,46,47) as well as against small cell lung cancer (SCLC) *in vitro* and in animal models (48,49,50,51).

Short term daily subcutaneous administration of AMD3100 for up to 7 days in humans for stem cell mobilization is well tolerated (52), but when administered as a daily IV infusion or subcutaneous injection for 11-14 days, as an HIV treatment in humans, it was associated with cardiac toxicity (53,54). MSX-122, also developed for stem cell mobilization, is a partial CXCR4 antagonist which in animal studies appears to be tolerated in longer term regimens, however, MSX-122 has not as yet been tested in humans.

Heparins are effective inhibitors of CXCL12. Recently, UFH has been shown to inhibit CXCL12 in a manner not dependent on its anticoagulant activity (42). Binding of heparin

produces a steric hindrance of CXCR4 binding to CXCL12 (55) when this negatively charged glycosaminoglycan binds to a concentration of cationic amino acids that overlap with the CXCR4 binding site (55). However, even greater effectiveness might be achieved using, CX-01, a low anticoagulant heparin, that would enable effective CXCL12 blocking without the risk of anticoagulation.

4.2 Study Rationale for CX-01 in AML

CX-01 is a rationally engineered complex carbohydrate derived from heparin that may represent a safer inhibitor of the CXCL12/CXCR4 axis.

Differential anticoagulant effect relative to heparin: Heparin is more than 200 fold more potent than CX-01 as an anticoagulant. The anticoagulant effect of CX-01 begins to appear at a plasma concentration that is approximately 2-fold higher than the plasma concentrations achieved in normal volunteer and patient studies (25 µg/mL); at these concentrations it is anticipated that CX-01 can be employed clinically with little if any anticoagulant effect (56).

Reduced antigenicity relative to heparin: HIT is a potential clinical complication of heparin administration that results from the formation of an antibody to the PF4/heparin complex, which in turn may cause thrombocytopenia and thromboembolism (57). CX-01 binds PF4 with an affinity similar to heparin, but the CX-01/PF4 complex does not activate platelets because it does not bind HIT antibodies and, unlike heparin/PF4, does not stimulate additional antibody production (56,58,59).

Platelet and white blood cell (WBC) recovery following chemotherapy: In patients with metastatic pancreatic cancer receiving gemcitabine + *nab*-paclitaxel, and in patients with AML receiving induction therapy with idarubicin and cytarabine, CX-01 appears to accelerate both platelet and WBC recovery after high dose chemotherapy. The acceleration of platelet and WBC recovery may be explained by a blocking effect of CX-01 on the inhibitory action of PF4 in marrow myeloid and megakaryocyte development after chemotherapy (60,61,62). In separate but related research, Cantex is collaborating with the National Institute of Health and other federal agencies to develop CX-01 as a medical countermeasure to radiation poisoning, where refractory thrombocytopenia is a major concern.

Thus, CX-01 may offer benefits to AML patients without the risks of other heparin derivatives, namely blocking of the CXCL12/CXCR4 axis without the accompanying risks of anticoagulation or of HIT; it may also benefit AML patients receiving intensive chemotherapy by accelerating platelet and WBC recovery times.

4.3 Summary of Studies with CX-01

4.3.1 Preclinical Data

In rats the no-observed-adverse-effect-level (NOAEL) was 48 mg/kg/day, and in dogs it was 160 mg/kg/day. The only observed adverse effect in either species was the expected

occurrence of hemorrhage at high doses of drug, when coagulation parameters were prolonged. No adverse effect on cardiac conduction has been observed in porcine studies of myocardial infarction. There were no adverse effects of CX-01 administration on the cardiovascular profile in dogs or on the respiratory parameters in albino rats.

4.3.2 Clinical Data

As of October 9, 2015, a total of 188 patients had been exposed to CX-01 at doses of 4 to 20 mg/kg as a bolus and doses of 0.125 to 3.9 mg/kg/hour as a continuous IV infusion for durations of 12 to 168 hours.

- 54 healthy subjects who participated in three phase I trials
- 78 subjects with exacerbation of chronic obstruction pulmonary disease (COPD) in a phase II study
- 35 patients with metastatic pancreatic cancer
- 5 patients with exacerbation of protein losing enteropathy (PLE) secondary to Fontan procedure (phase II study)
- 12 patients with AML
- 4 pediatric patients with recurrent solid tumors.

Table 4—1 Clinical Data in Conditions Other than Acute Myeloid Leukemia

Study Number	Phase	Indication	Number of Patients	Study Drug and Dose	Study Endpoints	Study Results
PGX-ODSH-2013-AML-1	Pilot	AML	N=12	Cytarabine at 100 mg/m ² /day as a continuous infusion for 7 days; Idarubicin 12 mg/m ² daily for 3 days; CX-01 given as a 4 mg/kg bolus followed by 6 mg/kg/day as a continuous infusion for 7 days (168 hours)	
Primary
 
 Safety and tolerability of CX-01 when combined with chemotherapy Obtain preliminary evidence of the effect of CX-01 on platelet transfusion independence 
Secondary Effect of CX-01 on CR rate, platelet nadir count, number of platelet transfusions, induced side effects
	
Combination was associated with CR rate of 92%. Hematologic recovery was rapid. Even though a small population was treated, data suggests that CX-01 could not only be a chemotherapy sensitizer for traditional 7+3 induction therapy but could also accelerate count recovery after induction.
 
CX-01 was found to be safe and well tolerated with no unexpected SAEs.

PGX-ODSH-2006	II	Exacerbation of COPD	N=156, equally randomized to receive standard treatment of COPD with or without CX-01	CX-01 given as a 8 mg/kg bolus followed by CX-01, 0.375 mg/kg/h for 96 hours	
Primary Composite of failure to discharge from hospital in a timely manner + relapse within 21 days of hospital discharge
 
Secondary FEV₁, FEV₁/FVC, Borg CR10Scale, 6-minute Walk Test, BODE index and hs-CRP
	
There was no evidence of effect or efficacy of CX-01 compared to placebo for the primary endpoint for Intent-to-Treat (ITT) or Per Protocol (PP) Populations. No statistical significant effects were shown for the secondary endpoints.
 
CX-01 was well tolerated. A few instances of minor/moderate bleeding and only one case of major bleeding. Some predictable changes were noted for AST and ALT with CX-01 treatment. No other clinical and laboratory parameters showed

Study Number	Phase	Indication	Number of Patients	Study Drug and Dose	Study Endpoints	Study Results
						significant changes from baseline. Eight deaths were reported (placebo=5 and CX-01=3). Those three were not related to CX-01 occurred post treatment.
PGX-ODSH-2009-PLE	II	Protein losing enteropathy (PLE) secondary to Fontan procedure	N=5, Pediatric and young adult population	CX-01, 96 hour IV infusion at 0.125 mg/kg/h or CX-01, 96 hour IV infusion at 0.250 mg/kg/h	Safety, reduction of symptoms of PLE, reduction of alpha-1 antitrypsin levels	Though all patients had some subjective clinical improvement, CX-01 did not show clear effects on efficacy biomarkers. Due to extremely low patient enrollment and a lack of efficacy, the study was terminated early. 22 AEs and two unrelated SAEs were reported. All AEs were considered mild or moderate in intensity.
PGX-ODSH-2011-PC	II	Metastatic pancreatic cancer	N=60, with 35 patients receiving CX-01 in conjunction with chemotherapy and 25 randomized to receive chemotherapy alone	Gemcitabine (1000 mg/m ²) and nab -paclitaxel (125 mg/m ²) on days 1, 8, and 15 for 3 weeks with or without CX-01 (4 mg/kg bolus followed by CX-01, 0.375 mg/kg/h for 48 hours) starting with the first dose of chemotherapy on Days 1, 8, and	Primary Progression-free survival (PFS)	No statistically significant change of PFS and OS was noted in patients receiving CX-01. Comparing Day 1 and Day 15 platelet counts in patients receiving gemcitabine + nab -paclitaxel with or without CX-01; a statistically significant increase was observed favoring CX-01 treatment. Among the 35 patients in this study treated with CX-01, 3 serious adverse events (pulmonary embolus, type II diabetes, and Grade 2 peripheral edema) were reported. The thromboembolic events were considered to be related to Trousseau's syndrome and underlying

Study Number	Phase	Indication	Number of Patients	Study Drug and Dose	Study Endpoints	Study Results
				15		disease.

Abbreviations: AE=adverse event, ALT=alanine aminotransferase, AML=acute myeloid leukemia, AST=aspartate aminotransferase, COPD=chronic obstruction pulmonary disease, CR=complete remission, FEV₁=forced expiratory volume in 1 second, FVC=forced vital capacity, hs-CRP=high sensitivity C-reactive protein, ITT=Intent-to-Treat, IV=intravenous, N=number, OS=overall survival, PFS=progression-free survival, PLE=protein losing enteropathy, PP=Per Protocol, SAE=serious adverse event. Note: Further details can be found in the Investigator's Brochure (63).

5. STUDY OBJECTIVES

This randomized, phase II study of CX-01 is designed to assess the effect of adding CX-01 at one of the two different dose levels to standard induction and consolidation therapy for newly diagnosed patients with AML.

5.1 Primary Objectives

The primary objectives are:

- To assess whether CX-01, administered at any or all studied dose levels in conjunction with standard induction therapy for AML increases the morphologic CR rate based on International Working Group (IWG) criteria
- To assess the safety and tolerability of CX-01, administered at two studied dose levels in conjunction with standard induction therapy for AML.

5.2 Secondary Objectives

The secondary efficacy objectives are:

To assess whether CX-01, administered at any or all studied dose levels in conjunction with standard induction and consolidation therapy for AML improves:

- Event-free survival (EFS)
- Leukemia-free survival (LFS)
- Overall survival (OS)
- Composite CR rate: incidence of CR + CRi, which is CR without recovery of neutrophils and/or platelets (ANC may be $<1000 \mu\text{L}$ and/or platelet count $<100,000/\mu\text{L}$).
- Duration of morphologic CR
- 30-day mortality (in the induction cycle)
- 60-day mortality (in the induction cycle)
- 90-day mortality (in the induction cycle)
- Neutrophil recovery
- Platelet recovery.

6. INVESTIGATION PLAN

6.1 Overall Study Design and Plan Description

This is an exploratory phase II, open-label, randomized, multicenter, parallel group trial to determine whether there is evidence that the addition of either or both different dose levels of CX-01 to standard induction therapy (idarubicin + cytarabine) and consolidation therapy has an additive therapeutic effect in newly diagnosed AML patients when compared to patients receiving standard induction chemotherapy alone.

Approximately 75 patients will be randomized in a 1:1:1 ratio to one of the following treatment groups:

- **Group 1:** Idarubicin + Cytarabine, OR
- **Group 2:** Idarubicin + Cytarabine plus lower dose CX-01 (0.125 mg/kg/hour), OR
- **Group 3:** Idarubicin + Cytarabine plus higher dose CX-01 (0.25 mg/kg/hour)

Eligible patients who meet the inclusion criteria and do not meet any of the exclusion criteria and have provided informed consent will be enrolled in the study. Each patient will participate in the study for approximately 18 months from the time of informed consent through final study contact, or until they withdraw from the study or the study is terminated by the Sponsor.

[figure not shown]
Overall survival data will be collected every 3 months until death or until the end of study by the investigational sites. The end of study will occur approximately 18 months after the last patient is randomized.

A Data and Safety Monitoring Committee (DSMC) will meet periodically to review the safety of the study (see Section 6.6.5). Details describing the DSMC process and procedures will be outlined in a separate DSMC Charter.

Adverse events (AEs) will be collected from time of informed consent and continue until 30 days after the last study treatment is administered. Longer follow-up and collection of AEs may be required for patients that do not have an absolute neutrophil count (ANC) recovery within 42 days (i.e., until the recovery or the reason for no recovery is diagnosed) after the last induction or consolidation cycle.

A flow diagram of the study design is shown in Figure 6—1.

Figure 6—1 Study Design

Abbreviations: AML=acute myeloid leukemia

Note: It is expected that approximately 90 patients will be screened to identify 75 patients for randomization.

6.2 Discussion of Study Design, Including the Choice of Control Groups

Approximately 75 patients will be randomized in a 1:1:1 ratio to receive standard induction and consolidation therapy with or without CX-01 at two different doses (lower and higher dose).

The anthracycline/cytarabine regimen using idarubicin (9-12 mg/m² daily) is considered a standard therapy for the majority of newly diagnosed patients with AML (64). Complete remissions are achieved in approximately 50% to 75% of patients (65). Dosing studies with continuous infusion cytarabine demonstrated that 100 mg/m² was as effective as 200 mg/m² (66,67).

The need for post remission therapy, following successful induction therapy, has been established in a number of clinical trials. It is presumed that most patients still have residual disease after the completion of induction chemotherapy (68). The standard treatment option includes consolidation therapy with intensive cytarabine-based chemotherapy regimens or allogeneic stem cell transplant.

6.3 Selection of Study Population

6.3.1 Inclusion Criteria

To be eligible to participate in the study, patients must meet the following criteria:

1. Newly diagnosed, *de novo* or secondary, previously untreated AML
2. Age 60 or above
3. Eastern Cooperative Oncology Group (ECOG) performance status of 0 to 2 (Appendix A)
4. Cardiac ejection fraction $\geq 45\%$ (as determined by echocardiography or multi gated acquisition [MUGA] scan)
5. Adequate hepatic and renal function determined by the following laboratory values:
 - Aspartate aminotransferase (AST) or alanine aminotransferase (ALT) $< 2.5 \times$ upper limit of normal (ULN)
 - Bilirubin $< 2.5 \times$ ULN
 - Calculated creatinine clearance by Cockcroft Gault formula > 30 mL/min (see Appendix C).
6. Able to provide informed consent and have signed an approved consent form that conforms to federal and institutional guidelines.

6.3.2 Exclusion Criteria

Patients who meet any of the following criteria will not be eligible to participate in the study:

1. Patients with acute promyelocytic leukemia based on the presence of t(15;17)(q22;q12) (69) as determined by karyotyping, fluorescence in situ hybridization or polymerase chain reaction
2. Prior chemotherapy for AML (including investigational therapy); prior hydroxyurea to control WBC count and a single intrathecal administration of cytarabine for CNS prophylaxis is allowed
3. Prior intensive chemotherapy or stem cell transplantation for treatment of myelodysplastic syndrome (prior treatment with hypomethylating agents and lenalidomide are allowed)
4. Presence of central nervous system leukemia
5. Presence of significant active infection that is not controlled in the opinion of the Investigator
6. Presence of significant active bleeding
7. History of severe congestive heart failure or other cardiac disease that contraindicates the use of anthracyclines, including idarubicin
8. Pre-existing liver disease (such as CHILD-Pugh Class B or C liver disease; see Appendix D)
9. Renal insufficiency which might adversely affect schedule and dose of therapy with cytarabine as well as management of tumor lysis syndrome.
10. History of drug addiction within the last 6 months
11. Known history of positive Hepatitis B surface antigens
12. Known history of positive test for Human Immunodeficiency Virus antibodies
13. Psychiatric or neurologic conditions that could compromise patient safety or compliance, or interfere with the ability to give proper informed consent
14. History of other active malignant disease within the past 3 years, other than cured basal cell carcinoma of the skin, cured in situ carcinoma of the cervix, or localized prostate cancer that has received definitive therapy. Such prostate cancer patients who are receiving hormonal therapy are eligible
15. Patients receiving any form of anticoagulant therapy (heparin flushes for IV

catheter permitted)

16. Presence of a known bleeding disorder or coagulation abnormality (including but not limited to aPTT >40 seconds) or any condition that requires maintenance of platelet counts at 50,000/ μ L or higher
17. Pregnant or breast feeding patients
18. Patients of childbearing potential not using adequate contraception.

6.3.3 Withdrawal and Discontinuation of Patients

Patients are free to withdraw consent and/or discontinue participation in the study at any time, without prejudice to further treatment. A patient's participation in the study may also be discontinued at any time at the discretion of the Investigator or Sponsor.

The following may be justifiable reasons for the Investigator or Sponsor to discontinue a patient from treatment:

- The patient was erroneously included in the study (i.e. was found to be ineligible)
- The patient experiences an intolerable or unacceptable AE
- The patient is unable to comply with the requirements of the protocol
- The patient participates in another investigational study without the prior written authorization of the Sponsor or its designee
- The patient's participation in the study presents a significant safety concern.

Patients who experience Grade 4 increases in AST, ALT or bilirubin (e.g., increase in AST or ALT >20 x ULN; increase in total bilirubin to >10 x ULN) will be discontinued from the study, if the Investigator judges that the laboratory abnormalities are potentially related to study treatment. Patients discontinued for this reason will not be re-challenged and will be followed until resolution of abnormal liver function tests.

Patients who are discontinued from study due to an AE will be closely monitored until the resolution or stabilization of the AE.

Patients who received at least one dose of study drug and who are discontinued from treatment, but not withdrawn from the study, will be asked to complete all evaluations for early termination (Early Termination/End of Study Visit).

Patients who discontinue from the study will not be replaced.

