- If Grade 4 increases in AST, ALT, or bilirubin occur (e.g., increase in AST or ALT to >20 x ULN; increase in total bilirubin to >10 x ULN) and if the Investigator judges that the laboratory abnormalities are potentially related to study treatment, the patient must discontinue study treatment immediately and will not be re-challenged. The patient will be followed until resolution of abnormal liver function tests.
- Renal function:

If the calculated creatinine clearance drops below 30 mL/min/1.73m² prior to or during dosing with CX-01, the dose of CX-01 will be held until the creatinine clearance rises above 30 mL/min/1.73m².
- For any other Grade 3 or 4 toxicities that appear to be related to CX-01 during either the induction or consolidation cycles, CX-01 will be interrupted until the AE resolves to Grade 1 or less, and then resumed at 0.125 mg/kg/hour provided administration of chemotherapy is in progress. If CX-01 is interrupted for greater than 72 hours, the patient will be discontinued from treatment. If the AE recurs at a level of Grade 3 or higher, the CX-01 will be discontinued.

This study will utilize the National Cancer Institute-Common Terminology Criteria for Adverse Events (NCI-CTCAE) Version 4.03 for AE and SAE reporting. A copy of the CTCAE Version 4.03 can be downloaded: (<http://safetyprofiler.ctep.nci.nih.gov/CTC/CTC.aspx>).

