6.8.3 General Considerations

The following is an overview of the statistical analysis methods to be used in this study. Details on the statistical analyses will be given in the Statistical Analysis Plan (SAP). Patients will be randomized to one of the following treatment groups in a 1:1:1 ratio:

- **Group 1**: Idarubicin + Cytarabine, OR
- **Group 2**: Idarubicin + Cytarabine plus lower dose CX-01 (0.125 mg/kg/hour), OR
- **Group 3**: Idarubicin + Cytarabine plus higher dose CX-01 (0.25 mg/kg/hour)

Unless stated otherwise, descriptive summary statistics will include frequency counts and percentages for categorical variables and number of observations, mean, standard deviation (SD), median, minimum and maximum and the 1st and 3rd quartiles for continuous variables.

The final analysis will be done when the last patient completes the study treatment, all assessments for disease response, and a Safety Follow-Up Visit approximately 30 days after termination of study treatment. All patients will be followed for OS for at least 18 months. Statistical analysis will be performed using SAS; the version used will be specified in the SAP.

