7. RISKS AND BENEFITS

The potential risks associated with participation in this study are minimal based on available safety data. Such risks are limited to unforeseen adverse interactions between idarubicin + cytarabine and CX-01. Heparins, as a class are associated with abnormal LFTs, which are generally reversible and of little clinical importance.

Study participants may benefit from participating in the trial if, by mobilizing AML stem cells from the protective environment of the bone marrow or through other mechanisms, the addition of CX-01 at either of two dose levels results in an enhanced cytotoxic effect of idarubicin + cytarabine, although such benefit is not guaranteed.

For further details concerning warnings, precautions, and contradictions, refer to the appropriate section of the IB (63).

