3 EFFICACY AND SAFETY VARIABLES

3.1 Primary Efficacy Endpoint(s)

The primary endpoint is the rate of patients in each treatment group achieving morphological CR based on IWG criteria during the induction and re-induction phases of the treatment. Morphologic CR is defined as ANC >1000/ μ L, platelet count >100,000/ μ L, <5% blasts in a bone marrow aspirate sample, no blasts with Auer rods, and no evidence of extramedullary disease (see Appendix A of protocol). Note that a patient is only considered to have achieved morphologic CR if this is documented on or after 21 days from date of randomization and not superseded by a subsequent data entry within 42 days of randomization that indicates treatment failure or progressive disease or persistent disease as indicated by >5% blasts in a bone marrow aspirate sample.

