6.2 Handling of Dropouts or Missing Data (where applicable)

For ITT analysis, patients with partial or missing data to determine morphologic complete remission on the eCRF form will be considered as not having met the criteria morphologic complete remission. For PP analysis and elsewhere, only the complete cases will be analyzed and no missing value imputation will be carried out.

Incomplete AE-related dates will be handled as follows:

- In cases where:
 - o the onset date is completely missing or
 - o the onset is in the same year (only the onset year is available) as the start of study treatment or
 - o the onset is in the same month and year (only the day is missing) as the start of study treatment or
 - o either the onset day or month is missing but the year is not before start of study treatment then the onset date will be replaced by the minimum of start of study treatment and AE resolution date.
- In all other cases the missing onset day or onset month will be replaced by first day or January.

Statistical Analysis Plan

Version: Final

Date of Issue: 20 March 2018

Cantcx Pharmaceuticals, Inc. Protocol No. CNTX-CX-01 2015 AML I Covance Study ID: 000000146201

- Incomplete stopping dates will be replaced by the last day of the month (if the day is missing only), unless this will result in a date after the date of death. If the imputed date will exceed the date of death, the date of death will be used as the stopping date. No imputation is needed if the event is ongoing.
- In all other cases the incomplete stopping date will not be imputed.

To impute missing day of follow-up dates (such as safety long term follow up) or Disease History, the missing day will be taken as the 15th of the month, as long as month and year is available. In all other cases missing or incomplete dates will not be imputed.

In patient listings, the documented date from cCRF will be reported (e.g. .May2016 in case where the day is missing, but month and year are available).

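### A patient stopped for a related Grade 4 liver test may miss the response marrow and be scored non-CR, because Protocol 6.3.3 and 6.4.4.2 differ and neither secures the assessment

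*Protocol*

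**What the plan says.** Protocol 6.3.3 and 6.4.4.2 both deal with a Grade 4 rise in AST, ALT or bilirubin that the investigator judges potentially related to study treatment.

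- **Protocol 6.3.3:** the patient "will be discontinued from the study, if the Investigator judges that the laboratory abnormalities are potentially related to study treatment". It continues: "Patients discontinued for this reason will not be re-challenged and will be followed until resolution of abnormal liver function tests".
- **Protocol 6.4.4.2:** "the patient must discontinue study treatment immediately and will not be re-challenged". Liver tests are again followed to resolution.

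Section 6.3.3 treats leaving treatment and leaving the study as different states. It has a separate rule for treated patients "who are discontinued from treatment, but not withdrawn from the study", who are asked to complete the early termination evaluations. Protocol 6.5.6 and the Early Term column of Table 6-1 list those evaluations: hematology, coagulation, chemistry, adverse events, concomitant medications, fibrinogen and D-dimer. Bone marrow is not among them.

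On the primary endpoint, SAP 3.1 says "a patient is only considered to have achieved morphologic CR if this is documented on or after 21 days from date of randomization". On missing response data in ITT, SAP 6.2 says "patients with partial or missing data to determine morphologic complete remission on the eCRF form will be considered as not having met" this endpoint. ITT is the primary efficacy set (SAP 5), patients who discontinue are not replaced (Protocol 6.3.3), and no sensitivity analysis is planned (SAP 7.6.3).

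**The concern.** Induction drugs run on Days 1 to 7. The marrow that decides re-induction falls on Days 14 to 21. Remission is evaluated at count recovery, or at about Day 35 (Day 49 after re-induction) if counts have not recovered (Protocol 6.4.1). A drug-related liver event can come before all of these. If the patient then leaves the study, or has only an Early Termination visit, the data needed to declare CR may never be collected. The ITT rule then records a failure that nobody observed.

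The loss need not be balanced. The trial is open-label and the trigger is an investigator's judgement of relatedness. Protocol section 7 notes that "Heparins, as a class are associated with abnormal LFTs", and the COPD study in Table 4-1 reports AST and ALT changes with CX-01. At stake is a small, toxicity-driven loss of primary endpoint data, more likely in the CX-01 arms, in a comparison with 25 patients per arm.

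There is also a smaller effect on the supporting analysis. SAP 5 treats keeping a patient on study against the withdrawal criteria as a deviation for the Per Protocol set. A site following 6.4.4.2 could therefore be recorded as deviating from 6.3.3.

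**Working it through.** **Step 1. Compare the two routes after a related Grade 4 liver event in induction.**

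| | Protocol 6.3.3 | Protocol 6.4.4.2 |
|---|---|---|
| What stops | Study participation | Study treatment |
| Follow-up named | Liver tests to resolution | Liver tests to resolution |
| Next visit | Not stated | Early Termination, through the general rule in 6.3.3 |
| Marrow at that visit | Not applicable | None (6.5.6, Table 6-1) |
| Response marrows explicitly kept | No | No |

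The bone marrow entries in Table 6-1 and its note 14 carry no on-treatment condition, so a site following 6.4.4.2 could still do them. Nothing tells it to, and the Early Termination instruction points the other way.

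**Step 2. Reproduce the planned power.** Inputs from Protocol 6.8.1 and SAP 2.6: 25 per arm, CR 0.55 (control) and 0.80 (CX-01), Fisher exact test, one-sided 0.15. Let x be control CRs and y higher-dose CRs. The test rejects when P(H ≥ y) ≤ 0.15, with H hypergeometric (50 patients, x + y responders, 25 drawn). Power is the sum of Bin(x; 25, 0.55) × Bin(y; 25, 0.80) over the rejecting pairs. The result is 71.7%, against 71.8% stated. The same sum with 0.55 in both arms gives a false-positive rate of 10.0%.

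**Step 3. Lose k higher-dose patients.** The documents give no Grade 4 liver rate, so k = 0, 1 or 2 is an assumed range. If lost patients are scored non-CR, y is Bin(25 − k, 0.80). If they had been assessed, y is Bin(25 − k, 0.80) + Bin(k, r), where r is their assumed response rate. The loss due to non-assessment is the difference in power.

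| k | Scored non-CR | Assessed, r = 0.55 | Difference | Assessed, r = 0.30 | Difference |
|---|---|---|---|---|---|
| 0 | 71.7% | 71.7% | 0 | 71.7% | 0 |
| 1 | 62.5% | 68.8% | 6.4 points | 65.9% | 3.5 points |
| 2 | 52.4% | 65.8% | 13.5 points | 59.8% | 7.4 points |

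With no true effect, losing 1 or 2 higher-dose patients lowers the false-positive rate from 10.0% to 7.3% or 5.2%.

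**Step 4. Lose patients in both arms.** With one patient lost per arm, power is 68.9% and the false-positive rate 9.6%, so little changes.

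**Step 5. See what one patient can do.** Against 14/25 control CRs, 19/25 gives one-sided p = 0.116 (pass) and 18/25 gives p = 0.189 (fail).

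**The case against.** The strongest reply is that the mismatch is one of wording, that the event is rare, and that neither section clearly ends data collection. Much of this stands, and it rules out four stronger readings that a reader might take from the text.

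- **That assessment depends on which section a site follows.** It does not clearly do so. Section 6.3.3 routes patients who stop treatment but stay on study to a visit without a marrow, so following 6.4.4.2 does not assure assessment either. The power differences above are due to non-assessment, not to 6.3.3 as against 6.4.4.2.
- **That a patient taken off study early cannot be a CR.** SAP 3.1 sets a date condition and no on-study condition. A later marrow that reached the eCRF could still count.
- **That 6.3.3 contradicts the survival follow-up.** Protocol 6.8.3 says "All patients will be followed for OS for at least 18 months". But 6.4.1 also takes patients off study for non-remission or transplant, and 6.8.3 makes no exception for them. Section 6.5.7 asks sites to make every effort to obtain long-term data. Being off study need not end survival follow-up.
- **That the false-positive rate is inflated.** Losing two controls and no higher-dose patient would give 16.2%, above the nominal 15%. That requires control patients to fall under the rule. The rule in 6.4.4.2 sits under CX-01 dose modifications, and its Grade 3 provision uses study treatment to mean CX-01. Only 6.3.3 read alone leaves control losses open.

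It is also true that CX-01 already stops at related Grade 3 (6.4.4.2), that chemistry is taken daily until discharge (Table 6-1 note 11), and that the 12-patient pilot reported no associated SAEs (6.4.4.1) at 6 mg/kg/day, which is 6 / 24 = 0.25 mg/kg/hour, the higher-dose infusion rate. Related Grade 4 events before response should be few. Scoring missing data as non-CR is a prespecified ITT rule and not an error in itself.

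What remains is that the two sections give different orders for one event and that neither says the response marrows continue.

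**Conclusion.** The point holds, and it is minor. A patient with a related Grade 4 liver event in induction may go unassessed for CR and be scored non-CR at a site following either section, with 6.3.3 the more explicit route.

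The size rests on assumptions: the number lost (0 to 2 higher-dose patients), planned CR rates for everyone else, and response of 0.55 or 0.30 in those lost had they been assessed. With none lost there is no effect. With 1 or 2 lost, non-assessment costs about 6 or 13 points of power at 0.55, or about 3 or 7 points at 0.30. The rest of the fall from 71.7% comes from those patients responding less often than 0.80, which no change of wording would recover. The likely direction is against CX-01, with a lower false-positive rate. The documents do not support a claim that the trial is biased towards CX-01.

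**What to change.** In Protocol 6.3.3, change the Grade 4 liver sentence from discontinuation from the study to discontinuation from study treatment, to match 6.4.4.2.

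Add one sentence: patients who stop study treatment for this reason still have the Table 6-1 marrows at Days 14 to 21 and at count recovery (or Day 42), the associated blood counts, and long-term follow-up, unless they withdraw consent. This sentence does the main work, because the change of wording alone would leave these patients with an Early Termination visit and no marrow.

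The cost is a few words and one sentence in one section. The marrows are already scheduled, so no procedure is added. Safety handling is unchanged: treatment stops at once, there is no re-challenge, and liver tests are followed to resolution. If no patient is lost, power stays at the reproduced 71.7%.
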